## 12.0 Data Management

Baseline demographic and clinical measures will be compared across groups using standard statistical methods (e.g., Chi square test of independence for categorical variables; Univariate ANOVA for continuous variables). Characteristics that (i) display imbalance at baseline, (ii) are associated with a dependent measure, or (iii) are known to be predictive of study outcomes (e.g., craving, smoking) will be assessed for inclusion as covariates in the final models. **Primary Aims Analysis:** The primary hypothesis of Aim 1 is that Group R-E will evidence decreased smoking behavior during follow relative to both control groups. Smoking behavior will be measured via smoking diary/TLFB recovered at each visit or by phone, from which, the mean CPD will be calculated between each visit for the period until the last attended visit. Additionally, the smoking diary/TLFB data will be used to compute an indicator of those that achieved a  $\geq$ 60% reduction in CPD relative to baseline smoking at each visit. Generalized linear mixed effects models will be used to analyze the longitudinal smoking behavior data during follow up (using appropriate

distributions). Overall statistical significance for the effects of treatment group, time, and their interaction will be assessed using a likelihood ratio test that compares the final model to a model consisting of an intercept term alone. The pre-specified hypothesis will be tested using model-based estimates to construct group comparisons across all the planned time points. Normality of residuals will be tested for models where appropriate and when found in error, appropriate transformations or non-parametric methods will be employed. Although mixed effects models have been proven highly efficient in cases where follow up data is missing at random, to accommodate other types of missing data, we will perform analyses using multiple imputation methods (Bayesian approach using both MCMC and FCS). The primary hypothesis associated with Aim 3 is that Group R-E will evidence decreased cue-elicited craving during follow-up testing. General linear mixed effects models will be constructed to assess group differences in craving over time. **Secondary Analysis:** Smoking relapse (i.e., days to 3 consecutive days of smoking ≥5 cigarettes) will be tested using a Cox Proportional Hazards regression model. Log-Log plots of the survival function and inclusion of a time variable treatment term will assess the proportionality assumptions and if models fail this assumption, a stratified Cox Regression model will be used. Also, we will measure end of study 7-day point prevalence abstinence as well as continuous abstinence using smoking diary/TLFB data. The effect of R-E training on abstinence outcomes will be tested using logistic regression models. **Biological Variables:** Exploratory analysis of sex effects on study outcomes will be assessed through main effects and the interaction between sex and study treatment assignment. Where significant interactions are found, sex stratified analyses will be conducted to assess the role of sex in the effect of RET on study outcomes. **Other secondary analyses** will assess i) differences between the control groups on main outcomes, ii) craving and cue reactivity differences during the three intervention sessions, and iii) the effects of treatment on ambient or background craving and cue reactivity (i.e., non-cue-elicited outcomes obtained early in test sessions). All analysis will be conducted using SAS/STAT v. 9.4 and Stata v. 14.

Validity and data integrity will be checked on an ongoing basis through the use of data audits. Study statisticians ([name]/[name]) will supervise quarterly data quality assessments (i.e., examination of the outcomes database(s) for missing data, unexpected distributions or responses, and outliers) performed by the study research staff. Accuracy and completeness of the data collected will be ensured by weekly review. A 10% random sample of the primary source document will be crosschecked with the database on a quarterly basis. If inaccuracies exceed 2%, then a second 10% will be randomly chosen for audit. Should data discrepancies be discovered, they will be resolved using original source documents. The REDCap system does not accept outliers, illogical response patterns, etc. The PI will have weekly meetings with the research staff to discuss qualitative comments received during data collection and any problems in data collection or entry. The statistician will periodically examine the database to look for irregularities. Initial data analyses will examine distributions of variable scores and comparability of baseline characteristics across conditions in case analyses need to be adjusted for these.

**fMRI Analysis Plan.** The hypothesis for 2a (CR) is that Group R-E will evidence attenuated CR in medial prefrontal cortex (mPFC: dorsal anterior cingulate-dACC; ventromedial: vmPFC), limbic regions (amygdala, hippocampus) and ventral striatum. Greater reduction in BOLD response in regions of interest will predict decreased smoking. fMRI data will be preprocessed using recommended procedures in SPM8 and as done previously. At the 1st-level, data will be analyzed using the GLM; events of interest (Smoking, Neutral) will be modeled as a boxcar canonically convolved hemodynamic response function, and HR and motion parameters entered as nuisance covariates. At the 2nd-level, 2 (Time: Pre, Post) x 2 (Group: R-E, NR-E) ANOVA will be used within an *a priori* ROI mask (amygdala, hippocampus, mPFC, ventral striatum;  $p < .05$ , pFWE). **Hypothesis for 2b (rsFC)** is that group R-E will evidence strengthened rsFC in frontostriatal circuitry; weakened rsFC in frontolimbic circuitry and the magnitude of rsFC will be inversely related to craving and smoking (e.g., CPD). **fMRI data analysis plan.** Similar to our previous work along with in scanner heart-rate and respiration entered as covariates, rsFC will

be assessed using the conn13 SPM8 toolbox. Connectivity matrix for each seed (see ROI mask in 2a) will be entered into separate: 2 (Time: Pre, Post) x 2 (Group) ANOVA. Exploratory voxel-wise analyses are planned for 2a and 2b with specific focus on subdivisions of the insular cortex (cf., Addicott et. al., 2015).

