The above findings also point to the need to fully characterize the magnitude and duration of effects induced by RET. Specifically, the R21 findings suggest the possibility that the craving differences between the groups may have just begun to emerge at the 1-month time point. Also, while the group difference on self-report smoking was present throughout follow-up, CO corroboration occurred only at 1-month, suggesting that the difference in smoking may have become more firmly established during the latter 2-weeks of follow-up. The trend level data on the proportion of participants that achieved a 60% reduction from baseline smoking suggests the possibility that a difference might have emerged with sufficient time. Accordingly, the proposed study will have a substantially extended follow-up period (6-months) in order to better characterize the long-term effects of RET on craving and smoking behavior. Also, if the plan to increase the amount of RET has the expected effect(s), then an extended 6-month follow-up may permit a more thorough assessment of larger and lasting treatment effects.

Although not explicitly suggested by the R21 findings, it seems critical that our 'next step' study should endeavor to identify the neural mechanisms that mediate RET effects on craving and smoking reduction. The extant literature on mechanism involved in modifying associative memories has primarily focused on extinction training. Evidence from infrahuman and human research in aversive and appetitive extinction learning indicates that distinct MTL structures (i.e., hippocampus and amygdala) interact with the inhibitory frontostriatal (vmPFC-ventral striatum)

[figure not shown]
pathway in a dissociable manner to modulate conditioned stimulus-unconditioned stimulus (CS-US) associations. The amygdala is necessary for extinction learning—potentially through a habituation process—whereas the hippocampus is necessary for memory integration and updating.

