
**ii. Participants:** A total of 166 treatment-seeking men and women smokers (83 per group), **aged 25 to 65**, will be enrolled. While we recruited smokers between the age of 21-65 in the R21, we have narrowed the age range in the proposed study in the interest of mitigating concern about the potential confounding effects of brain development in younger participants. Also, since more than 80% of smokers begin smoking before age 21, employment of this age range will ensure, even at the lower bound, that we are recruiting smokers with sufficiently long smoking histories to have well-established smoking-related memories. This age range also ensures the findings will be generalizable to the vast majority of smokers. Additional inclusion requirements are: a) smoke 10+ cigarettes/day for three or more years, b) be willing to make a cessation attempt, c) remain overnight abstinence prior to the baseline smoking cue reactivity assessment, and d) agree to comply with the reinforced abstinence regimen in place during the four laboratory sessions (3 intervention & 1 test). Prospective participants will be excluded if they meet DSM criteria for a psychotic disorder, severe major depression, bipolar affective disorder, substance dependence (other than nicotine) or have a neurological disorder/injury (e.g., dementia, brain tumor, Parkinson's disease, head injury).

**iii. Sample Size Estimation.** A sample of 166 participants assigned equally to 2 treatment groups will provide 80% power to detect clinically relevant reductions in smoking behavior while optimizing power ( $\geq 80\%$ ) to detect meaningful effects across the remaining hypotheses. Hypothesis 1a: In the R21 analysis, a greater reduction in CPD was seen in Group R-E as compared to Group NR-E (**Fig. 2b**: Cohen's  $d=0.5$ ). Since small studies are more likely to report larger effects than larger trials, we have designed this study to have at least 80% power to detect an effect of treatment on CPD with a 10% reduction from that observed in the R21 ( $d=0.45$ ). In the proposed study, we will measure CPD at each of 6 follow-up time points (**Fig. 6**). Under the assumption of independent observations, a total sample size of 78 participants randomized to each group will provide 80% power ( $\alpha < .05$ ) to detect an effect size of  $d=0.45$  between Group R-

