
**x. Test Sessions:** Participants will complete seven follow-up test sessions: 24-hours, 2-weeks and 1-month, 6-weeks, 2-, 3- and 6-months. We use monetary compensation to minimize test session attrition (only 17.2% of participants did not complete the R21). Consistent with the R21 and Xue et al., 2012, each test sessions will involve a CR assessment identical to the baseline CR assessment described above except that a brief novel smoking picture cue sequence will also be presented. Importantly, some procedural elements will not occur in all test sessions. First, only the 24-hour follow-up test session will be performed under conditions of reinforced abstinence. The goal will be to assess the acute effects of the interventions under the same conditions of abstinence that occurred during the intervention. Participants will be encouraged to maintain their smoking abstinence at the conclusion of this session but will not be compensated for it (participants will be given a referral to the SC state Quitline, a free, anonymous service that supports abstinence). Second, for individuals randomized to the fMRI condition, the 24-hr test session is the only one in which an fMRI session (identical to the one in the baseline assessment) will be performed immediately after the initial CR assessment (cf., Fig. 6); those not assigned to the fMRI condition will remain in the CR laboratory and receive the same CR regimen as administered in the fMRI condition. Third, at the end of all but the 6-mo. test session, participants will receive a smoking diary in which to record the occurrence of both daily smoking and craving. A TLFB assessment of smoking behavior will be performed whenever diary data is not available; all but one of the R21 participants used their diary to collect smoking data as instructed. For those follow-up periods where more than 2-weeks elapse between visits (i.e., period between the 2 and 3 mo. follow-up visit and the period between the 3 and 6 mo. visit), study staff will phone contact participants every 2 weeks to collect diary data. Fourth, in all but the 24-hr. follow-up test session, expired CO and a saliva sample will be collected in order to biochemically corroborate, via CO and cotinine levels, self-report smoking/abstinence (salivary cotinine abstinence cutoff  $\leq$  15 ng/ml per SRNT Guidelines and CO abstinence cutoff  $\leq$  5 ppm). Assessment of the use of any nicotine products (e.g., e-cigarettes, dip, gum, patch) will be assessed at all follow-up visits. At study completion, debriefing will occur in which participant questions will be addressed and recommendations for additional cessation treatment will be provided.

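### Mean CPD stops at the last attended visit, so smoking reported by phone after that visit is, read literally, left out of the H1 analysis

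*Combined protocol and SAP*

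**What the plan says.** Section 12.0 (Primary Aims Analysis) gives the data source for H1: "Smoking behavior will be measured via smoking diary/TLFB recovered at each visit or by phone". The same sentence then sets the averaging window: "the mean CPD will be calculated between each visit for the period until the last attended visit".

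Section 10.0, item x (Test Sessions), describes the phone route. For the longer gaps between visits, "study staff will phone contact participants every 2 weeks to collect diary data". The gaps named are the "period between the 2 and 3 mo. follow-up visit and the period between the 3 and 6 mo. visit".

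Section 10.0, item iii (Sample Size Estimation), says that "we will measure CPD at each of 6 follow-up time points". Section 2.0, part C, gives the reason for the longer follow-up: "the proposed study will have a substantially extended follow-up period (6-months) in order to better characterize the long-term effects of RET".

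Three other statements matter. Section 12.0 compares the groups over all planned time points. It handles missing follow-up with mixed models and multiple imputation (MCMC and FCS). Section 10.0, item ix, says that participants who break abstinence on the second or third treatment day are kept so that a full intent-to-treat analysis is possible.

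**The concern.** The window for a self-reported outcome is tied to attendance at a laboratory visit, although the outcome is also collected without one. The 6-month visit is the last, so anyone who misses it has a last attended visit at month 3 or earlier. CPD phoned in after that visit falls outside the stated window, and no other section brings it back. The same happens to month 2 to 3 phone data when month 2 was the last visit attended.

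The rule also treats like data unequally. A participant who misses month 3 but attends month 6 keeps the month 2 to 3 phone reports. One who attends month 3 and misses month 6 loses the month 3 to 6 reports. Whether observed data count then depends on later attendance, a post-randomization event that could be related to relapse. The reports lost are those nearest to dropout, which do most to support a missing-at-random model. This sits badly with the stated intent-to-treat aim.

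**Working it through.** **Inputs.** From section 10.0, item iii: d = 0.45, 80% power, α = 0.05 (sidedness not stated; two-sided reproduces the plan), six CPD time points, AR(1) correlation with ρ = 0.9, 25% dropout, 83 per group. From section 10.0, item x: calls every 14 days in months 2 to 3 and 3 to 6.

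**1. The plan's own figures.**
- Independent observations: n = 2(1.960 + 0.842)² / 0.45² = 77.5, so 78. This agrees with "a total sample size of 78 participants randomized to each group will provide 80% power".
- AR(1) variance factor for a generalized-least-squares average over m time points: (1 + ρ) / [m − (m − 2)ρ]. With m = 6: 1.9 / (6 − 3.6) = 0.7917. Then 77.5 × 0.7917 = 61.4, so 62.
- Dropout: 62 / 0.75 = 82.7, so 83.

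The chain 78, 62, 83 reproduces. No stated figure is in dispute.

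**2. How much data per person.** Months 3 to 6 are about 3 × 30.4 = 91 days, and 91 / 14 = 6.5, so about six calls. This is 3/6 = half of follow-up time, 3/5 = 60% of the time added beyond the pilot study's one month, and one of the six CPD intervals.

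**3. How many people.** 0.25 × 83 = 20.75, so at most about 21 per group miss the 6-month visit at the planned dropout. At the pilot rates quoted in the protocol (17.2% and 19.4%), the maximum is 14.3 to 16.1 per group. The rule costs data only for those who also answered calls after their last visit. The documents do not give that fraction, so the range is 0 to about 21.

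**4. Contrast averaged over time, worst case.** Assume all 21 per group lose only the last interval.
- The five-interval factor is 1.9 / (5 − 2.7) = 0.8261.
- Information per group with all data: 83 / 0.7917 = 104.8.
- With the loss: 62 / 0.7917 + 21 / 0.8261 = 103.7, a ratio of 0.989.
- Power = Φ(0.45 × √(information / 2) − 1.960): 0.903 with all data, 0.900 with the loss.
- For comparison, 62 completers alone give 0.804, so the dropout allowance already covers more than this loss.

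**5. Months 3 to 6 alone, same worst case.** Power = Φ(0.45 × √(n / 2) − 1.960).
- n = 83: 0.83.
- n = 62: 0.71.
- The standard error rises by √(83 / 62) = 1.16.

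This step uses the last interval only. A mixed model would recover part of the loss from earlier intervals, so these figures bound the effect. Steps 4 and 5 also treat the six intervals as equally spaced, as a ρ = 0.9 per time point implies, although their lengths differ.

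**The case against.** The best defence is that the authors never meant to drop these data. Section 12.0 names phone reports as a source for CPD, the calls exist to gather them, and no section says that they are excluded. The cut-off may only describe where a participant's follow-up ends. This stands as a remark about intent. It does not change the text: the reference to the phone names a source, the next clause sets the time limit, and an analyst following the sentence would stop at the last attended visit.

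A second defence is that closing each interval at a visit keeps CPD beside a CO or cotinine value and avoids calling a part-interval mean the 6-month result. That would be a fair rationale, but the documents do not give it.

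A third is that mixed models and multiple imputation already deal with missing data. In part they do, and with ρ = 0.9 the earlier intervals carry much of the information. Neither is a reason to estimate values that were observed.

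The objections on size stand. The 25% covers all dropout from randomization to the end of the study, not late dropout. Nothing is said about how many people who miss the visit still answer the phone, or about whether absence is related to relapse or differs by group.

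**Conclusion.** The rule as written excludes observed primary-outcome data and should be changed. Its effect is limited. It touches between 0 and about 21 of 83 per group, under the planned 25% dropout and an unknown rate of phone response. It leaves power for the time-averaged H1 contrast essentially unchanged. It lowers precision for the month 3 to 6 estimate, with power for that interval alone falling from 0.83 to 0.71 at the very worst. Bias is possible if non-attendance is related to relapse, but the documents give no basis for its direction or size.

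A reader might infer more, and the documents do not support it:
- **That H1 is underpowered.** It is not; see step 4.
- **That a known number per group will lose data.** No such number can be derived.
- **That months 3 to 6 are the whole purpose of the extension.** Months 1 to 3 are also new relative to the pilot study.
- **That relapse and abstinence share the defect.** The cut-off is written for mean CPD only. Section 12.0 states none for those analyses or for the 60% reduction indicator, so no change to relapse censoring is shown to be needed.

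**What to change.** Replace the averaging rule in section 12.0 with wording such as: *Mean CPD for each interval will be computed from all diary/TLFB days obtained at a visit or by phone, through the last day with smoking data, whether or not the closing visit was attended. Only what was not observed will be modelled or imputed.* State that the 60% reduction indicator uses the same CPD data, for consistency.

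Add a sensitivity analysis restricted to intervals closed by an attended visit, and report the number of days behind each interval mean.

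The cost is a change of analysis wording and one extra model run, since the calls are already planned. The downside is small: some intervals will rest on fewer days and will lack a closing CO or cotinine value. The sensitivity analysis is there to show whether that matters.

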**Fig. 5**

34/group) will receive a second CR assessment in the fMRI scanner whereas the remaining participants (n=98; 49/group) will receive the equivalent CR experience except in the CR lab. Participants will be required to remain overnight abstinent (CO verified) for the baseline CR session; monetary incentives will reinforce compliance with abstinence. This abstinence requirement ensures that baseline data will be collected under the same conditions of abstinence that will prevail for the subsequent four sessions (3 intervention and 1, 24-hr. test). Following the baseline CR assessment, participants will plan their cessation attempt to begin the night before the first of four consecutive daily laboratory sessions (Days 2, 3, 4 & 5 in **Fig. 5**), again with monetary incentives for abstinence throughout (**Fig. 5** under compensated abstinence). The purpose of abstinence during these four sessions is to minimize the likelihood of strengthening smoking memories with nicotine reinforcement via at-home smoking. Group R-E will then undergo 3 daily sessions of RET consisting of 5-min 'retrieval' smoking video followed 10 minutes later by 1-hour of 'extinction' training consisting of four sequences of smoking-related cues (same as in R21). The first test session will be performed 24-hrs after completion of the third RET session; it will be identical to the baseline CR session (i.e., a participant that received lab-based CR followed by fMRI CR at baseline, will receive the same arrangement in the 24-hr. test) with the exception that the lab-based CR will be assessed to both familiar (as in baseline session) and novel smoking cues. The conclusion of the 24-hr. test session also marks the end of compensated abstinence. Follow-up (lab-based cue reactivity) test sessions will occur at the following time points: 2-weeks, 1-month, 6-weeks, 2-months, 3-months, and 6-months. All test sessions will involve assessment of CR to both familiar and novel smoking cues. Participants will use smoking diaries to record daily smoking behavior throughout the follow-up period. A 'no-retrieval' control group, Group NR-E, will receive the same treatment as above except the 'retrieval' video will contain neutral, not smoking content. Both groups will be treated identically beginning with the 24-hr test session through study completion. All follow-up test sessions (**Fig. 5**, last box) will be identical to the first (24-hr) test session except (a) there will be no compensation for abstinence, (b) there will be no fMRI lab session, (c) participants will use diaries to collect daily information about smoking and craving, and (d) salivary cotinine will be collected to permit biochemical verification of self-report smoking/abstinence.

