E vs. control groups. However, the sample size in a repeated measures design is reduced when assuming a 1st order autoregressive error covariance structure with rho=0.9 (previous studies range 0.80-0.95). The number of participants per group required to achieve this power is therefore estimated to be n=62; however, this number needs to be adjusted for dropout between randomization and end of study. While the R21 dropout rate was 19.4%, this study will include a longer compensated abstinence period and longer follow-up period, which may increase dropout to 25%. Therefore, **83 participants** will be randomized per group after adjusting for dropout. Secondary Hypothesis 1b: Studies have shown that smokers with larger reductions in CPD may have increased odds of cessation compared to those with smaller reductions. Preliminary analysis from the R21 showed that 52% of participants in Group R-E had achieved a  $\geq 60\%$  reduction in CPD during the 2 weeks leading up to the 1 month follow-up visit relative to the 2 weeks prior to study treatment while only 26% of Group N-RE achieved the same milestone. The randomized sample size of 83 participants per group (62 completers) will provide greater than 80% power ( $\alpha < .05$ ) to detect a similar difference between group R-E relative to each control group. Hypothesis 3: In the R21, cue-elicited craving was measured during post-treatment test sessions at 24-hrs, 2-wks and 1-mo. In the 1-mo test session, differences between R-E and NR-E groups emerged, showing a decrease in cue-elicited craving in Group R-E as compared to Group NR-E ( $d=0.44$ ). In the proposed study, data will be collected at each of the 7 test sessions (over 6-months) and we assume an attenuated effect size (for the same reason noted above for CPD) relative to the R21 findings ( $d=0.40$ ). Given a moderate Rho ( $=0.5$ ), the sample will provide greater than 80% power to detect an effect size of  $d=0.4$  between Group R-E and controls. Thus, the sample size of **83 participants per treatment group (n=166 total)** will provide sufficient power ( $\geq 80\%$ ; and  $\alpha < .05$ ) to detect clinically meaningful smoking efficacy and craving differences for group R-E compared to controls, after accounting for up to 25% dropout.

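### The overall likelihood ratio test is made against an intercept-only model, so a significant result is not evidence specific to treatment or treatment by time

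*Combined protocol and SAP*

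**What the plan says.** The primary analysis is in Section 12.0 (Data Management), under Primary Aims Analysis. The model class is set first: "Generalized linear mixed effects models will be used to analyze the longitudinal smoking behavior data during follow up". One overall test is then described. It is meant to give "Overall statistical significance for the effects of treatment group, time, and their interaction", and it will be "assessed using a likelihood ratio test that compares the final model to a model consisting of an intercept term alone".

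Two neighbouring statements matter. Baseline characteristics that are imbalanced, associated with an outcome or known to predict it "will be assessed for inclusion as covariates in the final models". The sentence after the overall test says: "The pre-specified hypothesis will be tested using model-based estimates to construct group comparisons across all the planned time points". Nothing makes those comparisons conditional on the overall test. No likelihood ratio test that drops only the treatment terms, or only the interaction, is described anywhere.

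**The concern.** A likelihood ratio test is a test of whatever the comparator leaves out. Here the comparator leaves out group, time, group by time and every covariate. The sentence attaches the result to treatment, time and their interaction, but a significant result cannot be attributed to treatment or to the interaction. If a covariate is in the final model, it is not a test of those three terms alone either.

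A change in cigarettes per day (CPD) shared by both arms is plausible. Section 10.0, item i, says: "The conclusion of the 24-hr. test session also marks the end of compensated abstinence". Follow-up therefore starts from a few days of paid abstinence and continues unpaid for six months. Prognostic covariates are also likely. The R21 analysis of CPD reported in Section 2.0 adjusted for baseline CPD, sex, years of regular smoking and negative affect.

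What is at stake is the reporting of a supportive result: a report could show a significant overall test as support for treatment when treatment did nothing.

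**Working it through.** **Inputs from Section 10.0, item iii:** 62 completers per arm, 6 follow-up CPD points, d = 0.45, and a first "order autoregressive error covariance structure with rho=0.9" ("previous studies range 0.80-0.95").

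**Not in the documents, so assumed:** normal outcome, complete data, AR(1) as the analysis covariance with one lag per visit, the same covariance in both models, and the sizes of trend and covariate effect.

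**1. The plan's own figure.** Two-sided 5%, 80% power: n = 2(1.960 + 0.842)²/0.45² = 77.5, so 78. The variance factor for the weighted mean of m = 6 AR(1) values is (1 + ρ)/(m − (m − 2)ρ) = 1.9/2.4 = 0.7917. Then 78 × 0.7917 = 61.75, so 62, and 62/0.75 = 82.7, so 83. The stated 78, 62 and 83 reproduce.

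**2. Degrees of freedom.** With categorical visit and no covariate, the final model has 1 + 1 + 5 + 5 = 12 mean parameters and the comparator has 1. The planned test has 11 df (5% critical value 19.68). Dropping only group and group by visit gives 6 df (critical value 12.59).

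**3. No treatment effect, shared linear trend.** The noncentrality is λ = 2n·x′R⁻¹x, where x is the trend centred on the intercept-only fit. Under AR(1), x′R⁻¹x = x₁² + Σ(xₖ − ρxₖ₋₁)²/(1 − ρ²). For a total trend of 0.3 SD, x runs from −0.15 to 0.15 in steps of 0.06. At ρ = 0.9 this is 0.0225 + 0.016605/0.19 = 0.1099, so λ = 124 × 0.1099 = 13.63. The noncentral chi-square on 11 df then gives 69% rejection. For the nested 6 df test, λ = 0.

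| Assumed total trend (SD) | 0 | 0.1 | 0.2 | 0.3 | 0.5 |
|---|---|---|---|---|---|
| Planned, 11 df, ρ 0.8 | 5% | 8% | 19% | 43% | 93% |
| Planned, 11 df, ρ 0.9 | 5% | 10% | 31% | 69% | 99.6% |
| Planned, 11 df, ρ 0.95 | 5% | 15% | 57% | 95% | 100% |
| Planned, linear time, 3 df, ρ 0.9 | 5% | 15% | 52% | 89% | 100% |
| Nested, 6 df, any ρ | 5% | 5% | 5% | 5% | 5% |

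The linear-time row shows that the point does not depend on categorical visit. Maximum likelihood fits to simulated data (1,000 per setting, ρ 0.9) gave 5.9%, 33.5%, 68.7% and 99.7% at 0, 0.2, 0.3 and 0.5 SD for the planned test. The nested test gave 5.5–7.2%, which includes some small-sample error.

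**4. No treatment effect, no trend, one baseline covariate.** Let the covariate correlate r with CPD at every visit (assumed) and be absent from the comparator. Then λ = 124 × r²/(1 − r²) × (2.4/1.9), on 12 df. For r = 0.3, λ = 124 × 0.0989 × 1.263 = 15.5, and the test rejects in about 74% of trials. For r = 0.5, λ = 52.2 and it rejects in essentially 100%. The simulated fits gave 71.2% and 100%.

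**5. A real effect, d = 0.45 at every visit, no trend, no covariate, ρ 0.9.** For both overall tests λ = (62/2) × 0.2025 × 1.263 = 7.93. Power is 41% on 11 df and 53% on 6 df. For the group contrast averaged equally over visits, the mean of the AR(1) correlation matrix is 0.8239, so the standard error is √(2 × 0.8239/62) = 0.163. Then z = 0.45/0.163 = 2.76 and power is 79%. The comparator costs about 11 points. The rest of the gap to 79% is the price of any overall test.

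**6. Disagreement with the H1 contrast (100,000 draws, ρ 0.9).** With no effect and a 0.3 SD trend, the planned test is significant beside a non-significant contrast in 64.5% of trials, against 3.7% for the nested test. With d = 0.45 and no trend, the planned test and the contrast disagree in 39.2% + 1.7% = 41% of trials, and the nested test and the contrast in 28.2% + 1.8% = 30%.

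**The case against.** Without covariates the sentence describes a coherent joint test. Time is one of the three effects it names. If CPD drifts, the joint null is false and rejection is correct, so the percentages in the table are power to detect time, not false-positive rates for a stated treatment claim. The treatment question is handled in the next sentence by comparisons that are specific to treatment and not gated. H1 concerns a group difference during follow-up and does not need a separate interaction test. All six CPD points fall after paid abstinence ends, so that switch is not itself part of the contrast among visits. Only later drift counts, and the documents give it no size.

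Most of this stands, and it is why the point is minor. What it leaves is that the plan puts treatment and the interaction under a test that cannot isolate either. With any covariate in the final model, the joint-test reading also fails, because a literal intercept-only comparator tests the covariate too. That covariates will enter is likely but not certain, since the plan only says that they will be considered.

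**Conclusion.** The concern holds, at minor severity. As written, the overall test can be significant because of time or a covariate alone, and the plan states no overall test specific to treatment or to treatment by time. The error rate of the H1 comparisons and the sample size are not affected. The harm is limited to a supportive result that could mislead a reader of the report.

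The rejection rates rest on assumed trends and covariate correlations, on a normal outcome with complete data, and on carrying the sample-size AR(1) correlation into the analysis. The plan allows other distributions and does not state the analysis covariance. The logical point needs none of these figures.

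**What to change.** Replace the intercept-only comparator with nested comparisons fitted by maximum likelihood, each keeping the same covariates and covariance structure as the final model:

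- Treatment: drop group and group by time.
- Interaction: drop group by time only.
- Time: drop time and group by time.

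The df are 6, 5 and 10 with visit as a six-level factor, or 2, 1 and 2 with one linear time term. The plan should say which coding applies. It should also say that these overall tests are supportive and that H1 rests on the pre-specified group contrast. That statement is still needed after the change, because an overall test and the contrast will sometimes disagree (30% of trials in the d = 0.45 setting above).

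The cost is a few sentences in Section 12.0, with no new data and no change to the sample size.
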